- All WBC with 3 to 5 part differential (by capillary and/or venous, respectively) will be obtained at the same time at each drawing when possible (approximately 9am to 12 pm) to avoid the confound of morning pseudoneutropenia and will be performed weekly for 6 weeks prior to clozapine and 6 months after clozapine. In participants who discontinue clozapine during the trial, weekly WBC/ANC measurements will be performed for an additional 4 weeks. The WBC and ANC at the two US sites will be performed by Lab Corp, which is fully licensed by the State of Maryland. The Laboratories Unit of the Maryland Department of Health and Mental Hygiene licenses laboratories and is responsible for ensuring federal certification of all laboratories located in Maryland, including federal certification in the Clinical Laboratory Improvement Amendments of 1988 Program, required for all clinical laboratory testing sites used in analysis of samples from US patients. WBC and ANC counts are calculated by automated cell counter by Lab Corp or by using The Athelas One lab using the Automated Haematology Analyzer .
- WBC and ANC at the Nigeria site will be performed in the well-equipped FNPHY Medical Laboratory using the Beckman Coulter (3 to 5 part differential) for automated counts with use of a microscope for manual WBC backup, under the direct oversight of [name], Head Medical Lab Technician. This laboratory routinely performs CBCs, is registered by the Medical Laboratory Sciences Council of Nigeria, the body for registration of diagnostic labs in Nigeria, and will abide by all requirements that are indicated when analyzing samples from Nigerian patients.
- WBC and ANC cutoff and reference criteria used for safety monitoring for clozapine are standardized in this protocol, so using different laboratories for these measurements are not of concern.
- If morning neutropenia occurs the afternoon (12-4pm) draw time is acceptable. The draw time will be documented.

Clozapine Blood Levels:

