- The DNA will be shipped from Nigeria to the MPRC using either Oragene DNA kits or Whatman FTA Elute Micro Cards. DNA is relatively stable and currently DNA is being shipped on other collaborative grants without problems.

CLOZAPINE DOSING:

- Following consent and prior to initiation of clozapine, eligible patients will have weekly WBC/ANC. During this period, patients will be registered with the clozapine manufacturer and other medications will be appropriately titrated. Patients may be inpatients or outpatients.
- Clozapine will be recommended to be prescribed twice daily (other regimens permitted). The dose will be titrated within a range of 200-900 mg daily. *We do permit* individualized dosing, as occurrence of neutropenia and agranulocytosis is not clozapine dose-related. See recommended titration schedule below. If a patient has not received clozapine for two days or more he/she will need to have their clozapine initial dose be reinstated.

Recommended Clozapine Titration Schedule (3 week)

This is only a recommended titration schedule. This can be modified if necessary.

Day 1:	12.5 mg BID (1/2 of the 25 mg tablet)	
Day 2:	25 mg AM, 0mg HS	
Day 3:	25 mg AM, 25 mg HS	Extra visit, vitals, side effect and safety check
Day 4:	25 mg AM, 50 mg HS	
Day 5:	50 mg AM, 50 mg HS	
Day 6:	50 mg AM, 75mg HS	
Day 7:	50mg AM, 100 mg HS	Visit, vitals, side effect and safety, WBC
Day 8:	50mg AM, 100mg HS	
Day 9:	100 mg AM, 100 mg HS	
Day 10:	100 mg AM, 100 mg HS	
Day 11:	50 mg AM, 200 mg HS	
Day 12:	50 mg AM, 200 mg HS	
Day 13:	100 mg AM, 200 mg HS	
Day 14:	100 mg AM, 200 mg HS	clozapine blood level will be drawn, visit, vitals, side effect and safety, WBC
Day 15:	125 mg AM, 200 mg HS	
Day 16:	125 mg AM, 200 mg HS	
Day 17:	150 mg AM, 200 mg HS	
Day 18:	150 mg AM, 200 mg HS	
Day 19:	175 mg AM, 200 mg HS	
Day 20:	175 mg AM, 200 mg HS	
Day 21:	200 mg AM, 200 mg HS	Visit, vitals, side effect and safety, WBC

The white blood cell count level is not related to the dose of the medication. The dose throughout the study will not be altered based on white blood cell counts, but if the white blood cell counts fall lower than the established monitoring parameters for each patient the patient may be discontinued from treatment.

MONITORING GUIDELINES:

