 - viii. Only with compelling clinical circumstances should you consider starting granulocyte colony stimulating factors. In this case either filgrastim daily at 480 mcg subcutaneously (SQ) daily until ANC is $> 1000 /\text{mm}^3$ or a single dose of pegfilgrastim 6 mg SQ. The study nursing staff will arrange for seeing the patient for injections. This will be determined with hematology consult ONLY. These subjects will have daily contact by phone with a research nurse. Growth factor use can be associated with fever so use only if directed by hematology.
 - ix. For all subjects whose ANC does not increase above $500 /\text{mm}^3$ 20 days after last dose of clozapine or hematology recommendation, there may be consideration of bone marrow aspirate and biopsy.
6. If a participant falls below $500/\text{mm}^3$ he/she will likely be discontinued from the study. In this case, the research team will contact the clinical teams to check on the status of the patient and the outcomes of the patient event will be recorded, however the participant will not continue to with study visits and assessments. Only if a participant is seen by the ER, admitted for infection symptoms or receives filgrastim or pegfilgrastim this will be documented as a serious adverse event (SAE) and information sent to all regulatory bodies.
7. If participant is rechallenged with clozapine, resume treatment as a new patient monitoring level once ANC $\geq 1000/\text{mm}^3$ or at least patient's known baseline.

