The University of Maryland Baltimore IRB-approved study protocol and consent form will be reviewed by the Ethics Committee at the Federal Neuropsychiatric Hospital Yaba, Lagos and the Howard University IRB. Any significant changes requested by the Ethics Committee or Howard University IRB would be re-presented to the UMB IRB. At the Nigerian site, these documents would bear the seal of the Federal Neuropsychiatric Hospital Yaba and will be downloaded from CICERO in Lagos for use in consenting study participants in Lagos. Howard University will also have their consent forms. Furthermore, the UMB IRB-approved consent forms will be translated into two indigenous Nigerian languages by a team of linguistic experts and back-translated to English by an independent team of linguistic experts. Thus, consent forms at FNPHY will be available in English, Yoruba, and Igbo at the Nigerian site.

Treatment:

We have developed a slow and standardized dosing titration to protect against side effects and promote tolerability. This titration is consistent with that approved by the FDA and is included in the methods section.

Medication Adherence:

Patients receiving >75% of their assigned medication will be considered adherent. Outpatient adherence will be monitored through weekly pill counts and participant interviews. Medications will be dispensed on a weekly basis and will only be dispensed after adherence is assessed and all other assessments are completed. Inpatient adherence will be monitored through inpatient medication records. If a patient is observed to have an adherence problem, this will be discussed with the patient and a plan formulated to bring the patient back into adherence. These monitoring procedures have been used in other MPRC studies and have resulted in high levels of adherence (~90%). Non-adherence (not receiving >25% assigned study medication) will be reason for termination from the study. Clozapine discontinuation for more than two consecutive days will need re-titration. If this happens more than once the participant will be discontinued from the study but may continue to take clozapine as per the local clinical team recommendations.

Development of New Onset Diabetes and Hyperlipidemia:

If a participant develops new onset diabetes and/or hyperlipidemia during the study, a consult will be called by the treating physician, and the participant will receive treatment according to the current guidelines.

Withdrawal Criteria:

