We have criteria for discontinuation of clozapine and the ability to continue regular monitoring. Participants can stop study drug and continue in the monitoring portion of the study.

- A. Clozapine Discontinuation Criteria (clinician and PI opinion, following are potential causes of discontinuation).

Symptom Worsening:

Either the treating psychiatrist, medically accountable physician, or the PI may determine that a patient is experiencing clinical worsening. Clinical worsening may be defined as the following: the subject is judged to be entering an exacerbation of his/her illness by the treating clinician; an increase of 3 or more points from baseline on a BPRS positive symptom item; an increase of 3 or more points from baseline on BPRS somatic concern, conceptual disorganization or hostility; or an increase of 2 or more points from baseline on the CGI global severity rating or in the case the CGI is at a ceiling for beginning, clinical judgment will be made. Transient rating changes do occur so the symptom increases must be accompanied by the clinician's feelings that they are entering exacerbation.

No symptom Improvement

Clozapine discontinuation may take place in the case of no adequate symptom response to clozapine and discontinuation is thought to be a better option. Response is defined as 20% improvement and a final score of ≤ 35 in total BPRS score or CGI ≤ 3 . These scores generally result in a response rate of approximately 68% with another 25% demonstrating partial response. We anticipate that 7% of patients may not achieve any response (partial or full) and may be discontinued.

Low White Blood Cell Count

If a participant drops below 500 cells/mm³ (with stat redraw for confirmation) than clozapine will be discontinued. Participants may be discontinued due to a rapid falling white blood cell count if the hematologist or PI has reason to be concerned at a higher level.

Significant Side Effects.

The clinical and research team may discontinue clozapine if the participant is having significant side effects or side effects that are not in the best interest of the patient to continue for safety reasons. This will be determined by the research study team along with clinical team.

Medication Nonadherence

Clozapine discontinuation for more than two consecutive days will need re-titration. If this happens more than once as nonadherence the participant may be discontinued from clozapine

Non-adherent to Study Procedures

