If the participant is nonadherent to white blood cell monitoring, clozapine will be discontinued.

Once a participant is discontinued from clozapine, for whatever reason, they may remain in the study for continued monitoring.

B. Discontinuation from Study and all Monitoring:

- All attempts, as long as participant agrees, to follow-up monitoring when clozapine is stopped will occur
- Discontinuation from the study will occur if the participant is not adherent to study procedures and blood draws or if the participant no longer wants to be enrolled or the physician determines blood draws and/or study participation are not in the best interest of the patient
- If a patient is discontinued from open label clozapine for reasons described above, they will continue as usual for the follow-up lab work, symptom ratings and clozapine blood levels
- If the patient is recommended for clozapine discontinuation or study termination the PI or medically accountable physician will meet with the participant to describe why they are recommended for clozapine discontinuation or study termination.
- If the participant is discontinuing clozapine the research and clinical team will work together to ensure a plan for followed medication treatment in order to help with the appropriate titration of a new medication. This will be done clinically with no research protocol for cross titration and other medication treatment.
- If the participant is discontinuing clozapine but continuing in the study for monitoring no additional expectations are required
- When any participant is terminated from the study altogether, the study team will schedule with the participant as soon as possible to complete ratings and assessments (including laboratory tests and rating scales). This may result in a midweek visit. The participant will be compensated for any study visit time.
- If a participant is discontinued from clozapine they will continue, if they agree, to continue the follow-up monitoring for the entire 6 month treatment period.
- If a participant is nonadherent with blood work during clozapine they will be terminated from the study and no further data collection will occur past the final assessments.

BENEFITS:

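### After a second clozapine gap, two sections disagree on study status, and one of them ends study safety follow-up in participants who may still be taking the drug

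*Combined protocol and SAP*

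**What the plan says.** All references are to the combined protocol and SAP.

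- **Medication Adherence.** A clozapine gap of more than two consecutive days requires re-titration. Then: "If this happens more than once the participant will be discontinued from the study but may continue to take clozapine", on the advice of the local clinical team. A separate sentence says that missing more than 25% of assigned medication "will be reason for termination from the study".
- **Withdrawal Criteria, part A, Medication Nonadherence.** After the same re-titration sentence: "If this happens more than once as nonadherence the participant may be discontinued from clozapine".
- **Withdrawal Criteria, part B.** "Discontinuation from the study will occur if the participant is not adherent to study procedures and blood draws". The other grounds are the participant's wish and the physician's judgement. Dosing gaps are not listed. Participants taken off clozapine are, if they agree, "to continue the follow-up monitoring for the entire 6 month treatment period".
- **Laboratory Monitoring.** "In participants who discontinue clozapine during the trial, weekly WBC/ANC measurements will be performed for an additional 4 weeks".
- **Leaving the study** (Symptom Monitoring; Monitoring of adequate psychiatric symptom response; Withdrawal Criteria, part B). Completion ratings and laboratory tests are done where possible. No later ANC schedule is given.
- **Monitoring Guidelines, ANC <500 row, item 6.** Study visits will probably end, but "the research team will contact the clinical teams to check on the status of the patient" and the outcome is recorded.
- **Risk of Agranulocytosis - Analysis and Power.** Kaplan-Meier gives the six-month point estimate. A binomial upper 95% limit is also computed on all treated participants, whatever their length of follow-up.

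**The concern.** Two sections give different consequences for what is nearly the same event. One requires study exit and leaves the drug optional. The other makes stopping the drug optional and leaves study participation intact. Three sites in two countries have to apply this text, and they could treat the same participant differently.

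The Medication Adherence version is the one that matters for safety. It takes a participant out of study follow-up while expressly allowing clozapine to continue. Aim 3 is about the risk of agranulocytosis and serious infection on clozapine, so time on the drug is the time the study most needs to observe. A participant who comes off clozapine is, in most cases, offered more study ANC follow-up than one removed while still exposed.

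At stake is whether an event after such an exit would reach the study database. If it did not, the binomial limit would be too low, which is the unsafe direction.

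**Working it through.** **1. The two rules side by side.**

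- *Trigger.* Both start from more than one gap of more than two consecutive days. Withdrawal Criteria adds that the gaps must be nonadherence. The Medication Adherence sentence has no such qualifier, though it sits under an adherence heading. The rules therefore overlap for repeated gaps due to nonadherence.
- *Clozapine stopped after the second gap.* Medication Adherence: out of the study. Withdrawal Criteria: monitored to month 6, if the participant agrees. These conflict.
- *Clozapine continued after the second gap.* Medication Adherence: out of the study. Withdrawal Criteria, part A: no change in study status. These conflict too, and here the participant is still exposed.
- *Does part B settle it?* Its ground of nonadherence to procedures and blood draws does not clearly cover dosing gaps, because part A lists medication nonadherence and nonadherence to study procedures under separate headings. A participant with dosing gaps may attend every blood draw.

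**2. The plan's own figure.** Inputs: n=212 and zero cases (Risk of Agranulocytosis - Analysis and Power). The formula there is 0.05 = (1-r)^n, so r = 1 - 0.05^(1/212) = 0.01403, or 1.40%. The stated 1.4% reproduces.

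**3. One case instead of none.** The same section's equation with k=1 is 0.05 = (1-r)^212 + 212·r·(1-r)^211. The solution is r = 0.0222, or 2.22%. A single uncollected case would leave the reported limit at 1.40% when it should be 2.22%.

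**4. How likely such a case is.** The documents give no rate of second gaps, so the number of leavers still on clozapine, m, is an assumption: 5 to 20, leaving at about month 3. The risk comes from the historic non-BEN cohort in the same section: 0.9% at one year, with over 80% of cases in the first three months. At most 0.2 × 0.9% = 0.18% is left for months 3 to 12. The chance of at least one event after exit is 1 - (1-r)^m.

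- Ceiling, with all the remaining risk falling by month 6 (r = 0.0018): 0.90% for m=5 and 3.54% for m=20.
- Even spread over months 3 to 12 (r = 0.18% × 3/9 = 0.06%): 0.30% for m=5 and 1.19% for m=20.

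Earlier exits would raise these figures. The documents do not give the timing of cases within the first three months, so that increase cannot be computed from them.

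**The case against.** **The protocol points to the withdrawal section.** Symptom Monitoring refers readers there for more on discontinuation, and that section favours continued monitoring. This suggests which rule the authors may prefer, but it is a cross-reference, not a rule of precedence, and the mandatory removal sentence still stands.

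**Clinical monitoring goes on.** Participants exit to local care. Under Clozapine Dosing, "patients will be registered with the clozapine manufacturer", and US participants are enrolled in REMS. Events may well be detected clinically. This stands, and it limits the point to study ascertainment. The protocol does not provide for bringing those events back after this kind of exit, and the REMS provision is stated for US participants only, while about 130 of 250 are planned in Nigeria.

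**The loss of ascertainment is partly inferred.** Data collection after exit is expressly barred only for nonadherence with blood work. That is so. For leavers after repeated gaps, however, the text provides completion assessments and nothing further.

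**The binomial limit treats all dropouts this way.** It does, openly, and it is paired with Kaplan-Meier, which censors leavers and is valid if censoring is unrelated to risk. The limit is therefore not a flaw particular to this rule. The rule adds avoidable cases to it.

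Three stronger readings are tempting but not supported:

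- *Everyone who stops clozapine is followed longer than everyone removed while exposed.* Those stopped for ANC below 500 will probably end study visits, those nonadherent with blood work are terminated, and monitoring to month 6 needs agreement.
- *Those terminated under the 25% rule also stay on clozapine.* The text does not say so. One section expects prematurely terminated patients to resume other antipsychotics, and another allows either course.
- *The limit should be recomputed without participants of unknown status.* That would discard event-free follow-up which Kaplan-Meier already uses. Someone leaving after month 3 has passed the period holding over 80% of historic cases.

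**Conclusion.** The conflict is real and is in the current text. After repeated clozapine gaps, Medication Adherence requires study exit with the drug allowed, while Withdrawal Criteria permits stopping the drug and keeps the participant under monitoring. Followed as written, the first rule ends study collection of the Aim 3 safety outcomes in some participants still on clozapine.

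The expected numerical effect is small. It rests on an assumed 5 to 20 leavers, exit at about month 3, and the historic non-BEN risk applying to this population. A reader might infer that the agranulocytosis limit is materially biased as planned. The documents do not support that, because the most likely number of missed cases under these assumptions is zero. What remains is a low-probability error in the unsafe direction, in a study that expects few if any cases and where one case moves the limit from 1.40% to 2.22%. This is a cheap improvement, not a threat to the design.

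**What to change.** 1. Replace the removal sentence under Medication Adherence so that it agrees with Withdrawal Criteria: repeated gaps may end clozapine or scheduled ratings, but do not end safety follow-up.
2. For anyone still on clozapine after such an exit, and with the participant's agreement, obtain ANC<500 and serious-infection status to month 6 from the clinical team or clinical records, and from REMS records in the US. This extends the contact with clinical teams already described for exits after ANC below 500.
3. Report the number of participants with unknown month-6 status beside the binomial upper limit. Keep Kaplan-Meier as planned for the point estimate.

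The cost is a change to protocol and consent wording and modest record abstraction for the participants affected. No change to sample size or to the planned analyses is needed.

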Participants enrolled in the study at all 3 sites will receive the modified guidelines (table below) in addition to their informed consent and the investigator and patient will sign the consent acknowledging the modified guidelines. More stringent monitoring may take place if ANC levels fluctuate and modifications from this guideline may occur on a case by case basis with the consultation of a physician, hematologist and PI. During the study subjects will be very closely monitored as per below. Subjects will be educated concerning signs and symptoms of infection and the need to immediately report these throughout the study.

The Food and Drug Administration (FDA) has approved the modified monitoring procedures under an IND:

Absolute Neutrophil Count (ANC) Value	Modified Monitoring Plan Recommendation for Patients with History of or Current Benign Ethnic Neutropenia (BEN). Changes can be made with consultation from hematology. Always consider other medications that may be contributing to ANC suppression.
Clozapine Initiation	
 1. All patients initiating clozapine in the study will have had ANC <2500/mm³ in the past 24 months and those enrolled will not have a history of ANC<500/mm³. 2. Patients with two baseline ANC levels ≥1000/mm³ will be initiated with weekly blood draws. 3. Patients with baseline ANC levels between 500-999/mm³ may be initiated 
 a. After hematology consult and b. With specific oversight plan approved by hematology and study team. c. If initiated, patients will have ANC drawn twice weekly for first month of treatment prior to be considered for weekly monitoring. If ANC levels fall below 500/mm³, treatment will be interrupted as per protocol below. d. Justification for deviation from Risk Evaluation Management System (REMS) recommendations: We recognize that these are more lenient criteria than REMS, however, patients are enrolled in clinical trial with increased monitoring and we will be seeking a hematology consult and oversight prior to initiation and to make a plan for increased monitoring once treatment initiated.
ANC ≥1000/mm ³	Continue weekly ANC monitoring.

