ANC <1000/mm ³ to ≥500/mm ³	
 1. Continue clozapine treatment 2. Immediate redraw ANC to ensure second ANC value 3. Must contact hematologist at site or consultant hematologist. Provide hematologist with WBC/ANC history and review of medications. [name] MD, MHS Associate Professor of Medicine and Oncology Johns Hopkins School of Medicine [contact] [contact]. 4. If fever is present, will likely discontinue 5. Twice weekly ANC monitoring until ANC ≥1000/mm³ or at least patient's known baseline* 
 a. Justification for deviation from the REMS recommendations: We recognize that these are more lenient criteria than REMS, however, we will be undertaking a hematology consult and closely monitoring patients as per our clinical trial protocol 6. Once ANC ≥1000/mm³ or at least patient's known baseline, check ANC weekly
ANC <500/mm ³	
 1. Redraw immediately 2. Interrupt therapy for suspected clozapine-induced neutropenia 3. If fever, discontinue clozapine

4. Monitor ANC daily until $\geq 500/\text{mm}^3$, then twice weekly until ANC reaches patient's established baseline.
5. Must contact hematologist at site or consultant hematologist ASAP for plan of action similar to steps below:
 - a. Discontinue treatment is likely and most probable but will notify and consult hematology and make decision prior to discontinuation for $< 500/\text{mm}^3$ and no fever.
 - b. Possible Plan of Action with Consultation from Hematology and FDA:
 - i. Daily ANC until ANC $> 500/\text{mm}^3$
 - ii. Twice weekly CBC until ANC $> 1000/\text{mm}^3$
 - iii. Complete full history looking for signs and symptoms of infection.
 - iv. Subjects will continue with daily monitoring for fever.
 - v. If temp increases to $> 38.5^\circ\text{C}$, the subject will be directed to the Emergency Department or arranged for admission. If subject remains $< 500 /\text{mm}^3$, they may be admitted and covered with antibiotics for neutropenic fever according to institutional standards. Work-up may include blood cultures, urine cultures and chest x-ray as well as work-up for localizing symptoms if they exist.
 - vi. Once ANC increases to $> 500/\text{mm}^3$, antibiotics may be discontinued if no source of infection is identified.
 - vii. For subjects with recurrent, persistent fever after 48 hours of antibiotics, infectious disease consultation may be requested

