Pharmacy and General Overall Guidelines	
 1. All US participants will be registered the clozapine REMS program prior to initiation of clozapine. 2. US participants will be registered as BEN patients and, if necessary, the REMS program will be apprised of modified guidelines. 3. Clozapine will be dispensed as a seven day supply, so long as the ANC is at least 1000 to coincide with recommended blood draws. For patients whose ANC is > 500/mm³ and < 1000/mm³, medications may be dispensed as a three or four day supply based on appointment dates or as indicated below*. 4. If clozapine needs to be discontinued, participants will be contacted by phone or in person and advised to stop medication and come in for a follow-up visit. 5. A centralized research designee (clinical pharmacist) will coordinate with the dispensing pharmacy (if different than centralized) and physician involved with participant to ensure PDA is available where needed (outpatients) or that eligibility criteria is provided (inpatients). The centralized research designee clinical pharmacist shall act as designee for pre-identified prescribers working in the study. Per these guidelines, after physician review and approval, these specialized designees shall enroll patients and enter ANC levels for the study. 
 a. Justification for this deviation from REMS guide: All treatment decisions will be made by the prescribing psychiatrist after review of ANC and clinical criteria. Our specially trained clinical pharmacist is part of the clinical research team with advanced expertise in treating BEN patients with clozapine so highly qualified to accurately enter this information into the REMS system.
Other Information	
*daily, weekly or twice weekly blood draw and dispensing (particularly in the range of <500-<1000 /mm³) will be determined based on additional recommendations from the FDA, REMS implementation or based on individual patient parameters. Patients that remain between 500-1000/mm³ for longer than 4 weeks may be recommended for weekly clozapine blood draws and dispensing. Also going from twice weekly to weekly monitoring should occur after 4 values are back above 1000 cells/mm³ Emergency supply of two doses is given to all patients.

A patient version to give out at time of consent is included at the end of the protocol.

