The participant may choose not to participate in this study. If he/she chooses not participate in this study, their treatment at any facility or clinic including MPRC and Spring Grove Hospital will not be affected. Their continued care and treatment will not change if they choose not to take part in this study.

PARTICIPANT COMPENSATION:

During the first 6 weeks participants will have approximately 8 (or fewer) visits for screening and blood draws. During the last 6 months participants will have approximately 24 visits. Participants will be compensated \$20 per visit for their time for a total of approximately \$640 for participation in the study if they complete approximately 8 months. If any portion is completed participants will be paid only for the visits they completed. Participants will be paid by cash or check monthly and will also provided transportation to and from visits as needed.

PATIENT MONITORING

Absolute Neutrophil Count (ANC) Value	Modified Monitoring Plan Recommendation. Modifications may be made for each patient with hematology consult. Must be given to patient at time of consent. Patient Name _____ Date received _____
ANC ≥1000/mm ³	Continue weekly WBC monitoring.
ANC <1000/mm ³ to ≥500/mm ³	1. No Interruption of therapy 2. Redraw WBC to ensure second ANC value within range 3. Twice weekly WBC monitoring 4. Return to once weekly WBC monitoring when > 1000 /mm ³

WBC=white blood count, ANC=absolute neutrophil count

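### At ANC 500–999 the patient sheet says clozapine is not interrupted and gives no fever condition, while the investigator table for the same band makes discontinuation likely if fever is present

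*Combined protocol and SAP*

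**What the plan says.** Two tables in the combined protocol and SAP cover ANC below 1000 and at or above 500/mm³.

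- **Patient sheet (PATIENT MONITORING, end of protocol).** The header states "Must be given to patient at time of consent" and has fields for the patient's name and the date received. The first item in the band is "No Interruption of therapy". The other three are a redraw, twice-weekly counts, and a return to weekly counts above 1000. The header's only qualifier is "Modifications may be made for each patient with hematology consult".
- **Investigator table (MONITORING GUIDELINES).** It is introduced as FDA-approved under the IND. The first item in the band is "Continue clozapine treatment". It then requires an immediate redraw and contact with a hematologist, and item 4 reads "If fever is present, will likely discontinue". Twice-weekly counts follow.

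A note directly after the investigator table links the two: "A patient version to give out at time of consent is included at the end of the protocol". The opening paragraph of MONITORING GUIDELINES says that participants receive the modified guidelines, pointing to the table beneath it, and that "the investigator and patient will sign the consent acknowledging the modified guidelines".

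**The concern.** The sheet makes an unconditional statement about the very action that the fever item changes. A summary may leave out detail without contradicting its source. Here the omission turns a conditional instruction into an absolute one, in a paper that each participant is meant to keep.

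The band is not remote. RISKS AND DISCOMFORTS expects some participants to dip below 1000 during the study, and INFECTION MONITORING notes that infection can move quickly in neutropenic patients. For an outpatient, stopping depends on the site reaching the participant by phone or in person (Pharmacy and General Overall Guidelines row). Meanwhile the participant may hold a supply of three or four days, plus the emergency supply of two doses. If that call comes because of fever, the participant's own sheet disagrees with it.

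No estimate, sample size or analysis depends on this point. What is at stake is the accuracy of safety information given at consent and consistent handling across three sites.

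**Working it through.** No arithmetic applies: the plan gives no figure on this point and none is needed. The check sets the two tables side by side for the same band.

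| Element, ANC 500–999 | Investigator table | Patient sheet |
|---|---|---|
| Default action | Continue clozapine | Therapy not interrupted |
| Redraw | Yes, immediately | Yes |
| Counts | Twice weekly | Twice weekly |
| Hematologist contact | Required | Only a general header line on modifications |
| Fever present | Discontinuation likely | Nothing stated |

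**Step 1: where they agree.** Default action, redraw and count frequency match. Without fever the two tables lead to the same treatment.

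**Step 2: where they part.** Take ANC 700 with fever. The investigator table makes discontinuation likely; the sheet says there is no interruption. Both cannot describe what will probably happen to this participant.

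**Step 3: does the sheet's header close the gap?** Not fully. The header permits individual modification after hematology consult. The fever item is a standing condition for everyone in the band, and a reader of the header would not learn that fever bears on whether treatment continues.

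**Step 4: which paper does the participant hold?** The text allows more than one reading.
- If participants receive both tables, they hold two statements that differ on fever.
- If they receive only the sheet, they lack the fever condition.
- If they receive only the full table, the sheet's own instruction that it be handed over is not being followed.

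Each reading calls for reconciliation.

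**Step 5: is the row complete as read?** Its items run from 1 to 4 without a gap, so it appears whole. The sheet shows no row below 500, but that may be a loss in reading the PDF and nothing here rests on it.

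**The case against.** The strongest reply is that the sheet is a shortened patient version carrying the same default, labelled a recommendation, with a header that allows departures after hematology consult. Because the investigator table makes hematology contact mandatory in this band, a fever decision would usually arise within such a consult. That stands in part: it limits the conflict to febrile participants, but it does not put the fever condition on the sheet.

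The second reply is that other safeguards are strong. The Schedule of Events provides infection-reporting education at screening, before clozapine and weekly on treatment. INFECTION MONITORING has temperature and infection symptoms checked at every visit, tells participants to contact the physician at once, and requires a physician's evaluation of any fever. Counts in this band are twice weekly, and a physician can be reached around the clock. This also stands. Nothing on the sheet tells a participant to hold back a report of fever or to decide alone about stopping. These measures reduce the risk without correcting the statement.

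A reader might infer three stronger points, which the documents do not support.

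- **That the Withdrawal Criteria contradict the sheet as well.** The sentence there begins "Participants may be discontinued due to a rapid falling white blood cell count if the hematologist or PI has reason to be concerned at a", and the level it goes on to name is one above 500. This is general discretion, listed among potential causes and left to clinician and PI opinion. It is not a rule for this band.
- **That participants sign up to a rule the site will not follow.** On its wording, the acknowledgement refers to the modified guidelines in the full table, which contains the fever item. The consent form is not in the documents reviewed, so what it says about fever cannot be checked.
- **That participants in this band are seen only weekly and carry a week's supply.** That is the schedule for ANC of 1000 and above.

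**Conclusion.** The inconsistency is real and narrow. For ANC 500–999 with fever present, the patient sheet and the investigator table disagree on whether clozapine continues. In the same band without fever they agree.

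Its size cannot be given as a number of participants. One might assume that 10% to 40% of the 250 enter the band (250 × 0.10 = 25; 250 × 0.40 = 100) and call 25 to 100 people affected. The documents supply no such percentages, and that count would include everyone in the band, whereas the conflict touches only those who are also febrile. Their share is not stated.

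The conclusion assumes that the 500–999 row of the sheet was read in full and that the sheet is handed out as its header requires. It takes no view on which clinical rule is right. It is worth correcting because the sheet is a patient-safety document about stopping treatment and the remedy is cheap, but it is a consistency fault and not a flaw in the design.

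**What to change.** Reconcile the 500–999 row of the patient sheet with the same band of the investigator table on what happens when fever is present, so that both state one rule. The sponsor, the hematology consultant and the FDA should settle which rule that is. In the same revision:

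- state in MONITORING GUIDELINES which paper the participant receives and which one the signature acknowledges;
- check that the consent form agrees with the settled wording;
- if wished, add a cross-reference to the general discretion in the Withdrawal Criteria to stop for a rapid fall.

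The cost is a revised one-page sheet, IRB approval, and re-issue to participants already enrolled. Sample size, visits and analyses are unchanged.
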